5.4 Definition of Dose-Limiting Toxicity

Dose-limiting toxicity (DLT) will be assessed for the first cycle of treatment (6 weeks/42 days) at all dose levels.

A DLT is considered a treatment-related toxicity. Subjects who are withdrawn from the study before the completion of the DLT evaluation period in any phase for a reason other than a DLT will be replaced (NOTE: This includes subjects who may be removed during the blinatumomab-only run-in phase, prior to addition of nivolumab/ipilimumab). A toxicity with a clear etiology NOT related to a study treatment agent may not be considered a DLT; the Protocol Chair should be consulted in all cases.

DLTs include any grade 3 or higher non-hematologic toxicities which requires a subject to permanently discontinue protocol treatment during the DLT period as defined in Section 6.2.2 and 6.3.4 with the following exceptions:

- A) Any grade 3 or 4 drug-related laboratory abnormality or electrolyte abnormality that can be managed with electrolyte replacement, hormone replacement, insulin or that does not require treatment discontinuation
- B) Any grade 3 or higher toxicities that are frequent in ALL population such as fever, infection, bleeding, fatigue, bone pain, disseminated intravascular coagulation, tumor

lysis syndrome. Grade 4 infections which are felt by the PI to be primarily related to nivolumab ± ipilimumab administration or may have been exacerbated by nivolumab ± ipilimumab administration will be considered DLT. The PI and study team will closely monitor the cumulative rate of infections through the trial and in the expansion cohort to see whether the rate is higher than expected with blinatumomab alone.

- C) Any grade 3 or 4 event that occurs during the blinatumomab run-in period prior to the initiation of nivolumab or ipilimumab and requires permanent treatment discontinuation will not be considered a DLT. During the phase II trial based on which blinatumomab received FDA approval, 10% of patients permanently discontinued blinatumomab due to adverse events that were thought to be treatment-related and 18% of patients discontinued treatment due to adverse events.³² Thus adverse events requiring treatment discontinuation due to blinatumomab monotherapy are common and expected, so they should not be defined as DLTs in a trial to assess combination therapy.

For hematologic toxicity, the only adverse event that will be considered dose limiting is:

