6.3.2 Dose Delays

If treatment is delayed >6 weeks for an adverse event, the patient must be permanently discontinued from study therapy.

Patients requiring high dose steroid treatment for autoimmune or inflammatory events should go off study treatment except for a short course of tapering steroids for infusion reaction, skin rash or endocrine events.

Patients with grade 3 thyroiditis and skin rash may continue therapy as for grade 2 events with resolution and stable replacement treatment.

Patients with thyroiditis or hypopituitarism who are stable as above may be restarted with replacement hormones including thyroid hormone and physiologic doses of corticosteroids. Please note that hypophysitis with symptoms of headache, visual or neurologic changes or radiologic evidence of pituitary enlargement and other CNS events such as aseptic meningitis or encephalitis should be considered grade 3 events.

Any patients who require additional immune suppressive treatment beyond steroids should go off study treatment.

Patients requiring > two dose delays for the same event should go off protocol therapy.

Prior to starting corticosteroids or hormone replacement for any reason, appropriate endocrine testing including cortisol, ACTH, TSH and T4 must be obtained to document baseline.

Please note that in some cases the treatment algorithms recommend steroids if symptoms do not resolve in 7 days. However, this recommendation is not meant to delay steroid treatment at any time it is clinically indicated.

Patients may be dose-delayed for evaluation and restarted depending on results. Any patient started on corticosteroids initially who is determined to not require steroid treatment for an autoimmune adverse event may resume therapy after a 2-week observation period without further symptoms at the discretion of the PI or investigator.

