See GI AE Algorithm for management of symptomatic colitis. Patients with grade 2 symptoms but normal colonoscopy and biopsies may be retreated after resolution. Patients who require steroids should be taken off study treatment. Please evaluate pituitary function prior to starting steroids if possible without compromising acute care. Evaluation for all patients for additional causes includes C. diff , acute and self-limited infectious and foodborne illness, ischemic bowel, diverticulitis, and IBD.	
Recommended management: see GI AE management Algorithm	

Pancreatitis Amylase/Lipase	Management/Next Dose for Nivolumab and Nivo/Ipi Combination
Grade 2	Hold until baseline. Resume at same dose level if asymptomatic
Grade 3	Hold until baseline. Resume at same dose level if asymptomatic. Patients who develop symptomatic pancreatitis or DM should be taken off treatment
Grade 4	Hold until baseline. Resume at same dose level if asymptomatic. Patients who develop symptomatic pancreatitis or DM should be taken off treatment

Patients may develop symptomatic and radiologic evidence of pancreatitis as well as DM and DKA. Lipase elevation may occur during the period of steroid withdrawal and with other immune mediated events or associated with colitis, hepatitis, and patients who have asymptomatic lipase elevation typically have self-limited course and may be retreated. For treatment management of symptomatic pancreatitis please follow the Hepatic Adverse Event Management Algorithm
	

Pneumonitis	Management/Next Dose for Nivolumab and Nivo/Ipi Combination
Grade 1	Consider holding dose pending evaluation and resolution to baseline including baseline pO ₂ . Resume no change in dose after pulmonary and/or ID consultation excludes lymphocytic pneumonitis.
Grade 2	Hold dose pending evaluation. Resume no change in dose after pulmonary and/or ID consultation excludes nivolumab and associated lymphocytic pneumonitis as the cause of the pneumonitis. If nivolumab/ipilimumab related, hold until baseline. Patients must be stable off steroids for two weeks. Resume at same dose level.
Grade 3	Hold dose pending evaluation. Resume no change in dose after pulmonary and/or ID consultation excludes nivolumab and associated lymphocytic pneumonitis as the cause of the pneumonitis. If nivolumab/ipilimumab related, off protocol therapy.
Grade 4	Off protocol therapy

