
*Including CHF, LV systolic dysfunction, Myocarditis, CPK, and troponin
 
**Patients with evidence of myositis without myocarditis may be treated according as “other event”
 
Note: The optimal treatment regimen for immune mediated myocarditis has not been established. Since this toxicity has caused patient deaths, an aggressive approach is recommended.
	

Fatigue	Management/Next Dose for Nivolumab
≤ Grade 1	No change in dose.
Grade 2	No change in dose
Grade 3	Hold until ≤ Grade 2. Resume at same dose level
Grade 4	Off protocol therapy
Fatigue is the most common adverse event associated with immune checkpoint therapy. Grade 2 or greater fatigue should be evaluated for associated or underlying organ involvement including pituitary, thyroid, and hepatic, or muscle (CPK) inflammation	

Neurologic events	Management/Next Dose for Nivolumab and Nivo/Ipi Combination
≤ Grade 1	No change in dose.
Grade 2	Hold dose pending evaluation and observation. # Hold until resolves to baseline. . Off protocol therapy if treatment with steroids is required. Resume at same dose level for peripheral isolated n. VII (Bell’s palsy)^
Grade 3	Off protocol therapy
Grade 4	Off protocol therapy
*Patients with any CNS events including aseptic meningitis, encephalitis, symptomatic hypophysitis, or myopathy, peripheral demyelinating neuropathy, cranial neuropathy (other than peripheral n. VII^), GB syndrome, myasthenia gravis should be off study.	
Recommended management: See Neurologic Adverse Event Management Algorithm	

Endocrine Hypophysitis Adrenal Insufficiency	Management/Next Dose for Nivolumab and Nivo/Ipi Combination
≤ Grade 1	Asymptomatic TSH elevation* If asymptomatic continue therapy.
Grade 2	Hold until patients are on a stable replacement hormone regimen. If treated with steroids patients must be stable off steroids for two weeks. Resume at same dose level.
Grade 3	Off study treatment.
Grade 4	Off protocol therapy

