6.3.4 Discontinuation of Nivolumab/Ipilimumab Treatment

Nivolumab and ipilimumab treatment should be discontinued if any of the following criteria are met:

- Any grade 2 drug-related uveitis or eye pain or blurred vision that does not respond to topical therapy and does not improve to Grade 1 severity within the re-treatment period OR requires systemic treatment.
- Any adverse event, laboratory abnormality, or intercurrent illness which, in the judgment of the investigator, presents a substantial clinical risk to the subject with continued study drug dosing. **NOTE:** Any grade 3 or 4 drug-related laboratory abnormality or electrolyte abnormality that can be managed with electrolyte replacement, hormone replacement, insulin or that does not require treatment **does not** require discontinuation.
- Any adverse event that requires discontinuation of treatment per Section 6.3.3.
- Any subjects who require additional immune suppressive treatment beyond steroids should go off study treatment.
- Subjects requiring >2 dose delays for the same type of event should go off protocol therapy.
- Any dosing interruption lasting >6 weeks, with the following exceptions:
 - Subjects being tapered after high dose corticosteroids over one month followed by a two-week observation period will be allowed an additional two weeks to restart treatment (a maximum eight week interruption).
 - Dosing interruptions >6 weeks that occur for non-drug-related reasons may be allowed if approved by the Protocol Chair. Prior to re-initiating treatment in a subject with a dosing interruption lasting >6 weeks, the Protocol Chair must be consulted.

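### Discontinuation rules conflict for diabetes or insulin-managed hyperglycemia and for grade 3 hypopituitarism on replacement, and the DLT definition depends on them

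*Combined protocol and SAP*

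**What the plan says.** Section 5.4 states: "DLTs include any grade 3 or higher non-hematologic toxicities which requires a subject to permanently" discontinue treatment during the DLT period, "as defined in Section 6.2.2 and 6.3.4". Exception A removes from the definition "Any grade 3 or 4 drug-related laboratory abnormality or electrolyte abnormality that can be managed with electrolyte replacement, hormone replacement, insulin", among others. Section 6.3.4 lists as grounds for stopping any event that 6.3.3 says must stop treatment. Its NOTE then says that a grade 3-4 drug-related laboratory or electrolyte abnormality "that can be managed with electrolyte replacement, hormone replacement, insulin or that does not require treatment" does not require stopping.

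In 6.3.3, the pancreatitis table says at grades 3 and 4: "Patients who develop symptomatic pancreatitis or DM should be taken off treatment". The endocrine table, headed hypophysitis and adrenal insufficiency, says at grade 3: "Off study treatment".

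Section 6.3.2 says: "Patients with grade 3 thyroiditis and skin rash may continue therapy as for grade 2 events with resolution and stable replacement treatment". Its next sentence allows patients with stable thyroiditis or hypopituitarism to restart on hormone replacement, which may include corticosteroids at physiologic doses. That sentence gives no grade.

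**The concern.** DLT in cycle 1 is the endpoint that sets the MTD, and for non-hematologic events it is defined almost wholly by whether treatment must stop. A contradiction among the stopping rules is therefore a contradiction in the primary endpoint.

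The events are foreseeable. The adverse event lists in Section 7.1.1 name hyperglycemia for all three agents, diabetes with ketoacidosis for nivolumab, adrenal insufficiency for nivolumab and ipilimumab, and hypopituitarism for ipilimumab. The same DLT criteria drive the expansion stopping rule in 13.4.1, so an unclear classification affects both parts of the trial.

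**Working it through.** **1. The chain.** 5.4 sends the reader to 6.3.4 for what forces discontinuation, and 6.3.4 adopts the entries in 6.3.3. An off-treatment entry in 6.3.3 for a grade 3 or higher event is thus a DLT unless an exception in 5.4 applies.

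**2. The two groups.**

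| Event | Route to stopping, hence DLT | Route to continuing, hence no DLT |
|---|---|---|
| Grade 3-4 hyperglycemia treated with insulin | Recorded as DM: off treatment in the 6.3.3 pancreatitis table | Recorded as a laboratory abnormality: 6.3.4 NOTE and 5.4 exception A |
| Grade 3 hypopituitarism, including pituitary-related adrenal deficiency, stable on replacement | 6.3.3 endocrine table, grade 3 | 6.3.2 restart sentence, no grade stated |

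For the first group, no section says when insulin-treated hyperglycemia becomes DM, so the label decides the outcome. Section 6.3.4 itself holds both the adoption of 6.3.3 and the contrary NOTE. For the second group, the hormone-replacement wording of exception A and the NOTE is limited to laboratory and electrolyte abnormalities. Nothing says whether a hormone deficiency on replacement counts as one.

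**3. Events not in conflict.** The endocrine footnote in 6.3.3 lets thyroiditis be retreated on replacement and lets isolated thyroid or testosterone deficiency be handled as grade 2, which agrees with 6.3.2. Both sections class symptomatic hypophysitis or an enlarged pituitary as grade 3.

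**4. Effect of one event on the expansion rule.** Section 13.4.1 uses a Beta(1,2) prior and holds enrollment if Pr(risk > 0.30) is at least 0.70. After x DLTs in n patients the posterior is Beta(1+x, 2+n−x), and Pr(Beta(a,b) > 0.30) = P(Bin(a+b−1, 0.30) ≤ a−1).
- 2 of 4: Beta(3,4), so P(Bin(6, 0.30) ≤ 2) = 0.744, as the plan states. Its other four posteriors also reproduce (0.916, 0.837, 0.874, 0.806).
- With one DLT fewer, 1 of 4: Beta(2,5), so P(Bin(6, 0.30) ≤ 1) = 0.420, and enrollment continues.
- At the other four boundaries, one DLT fewer gives 0.652 (2 patients), 0.528 (3), 0.647 (5) and 0.552 (6), all below 0.70.

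**5. Effect on passing a dose level.** Sections 5.2.1 and 13.4 pass a level at no more than 1 DLT in 6. Two DLTs in the first 3 already exceed that limit, so P(pass) = (1−p)^6 + 6p(1−p)^5. The documents give no DLT rate for the disputed events, so every p here is an assumption.
- p = 0.20: 0.26214 + 0.39322 = 0.655
- p = 0.25: 0.17798 + 0.35596 = 0.534
- p = 0.30: 0.11765 + 0.30253 = 0.420

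From a 10% base, adding 5 or 10 points moves P(pass) from 0.886 to 0.776 or 0.655.

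**The case against.** **Exception A controls.** It is written as an exception, so a pure laboratory abnormality within it is not a DLT whatever 6.3.3 says. That stands, but it settles only events that are plainly laboratory abnormalities. It does not say whether DM or a hormone deficiency on replacement is one, and it leaves the instructions on continuing treatment in conflict.

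**DM and hyperglycemia are different terms.** True: 6.3.3 has no hyperglycemia row. But the protocol draws no line between the two when insulin is given.

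**The restart sentence in 6.3.2 may mean grade 2 only,** which would match the grade 2 endocrine row. That reading is possible. The sentence does not say so, however, and the stability it refers back to is described in the preceding sentence, which concerns grade 3. Section 6.3.2 also does not name adrenal insufficiency, so that event is in doubt only where it is part of hypopituitarism.

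**Review is central.** Section 5.4 calls for consultation with the Protocol Chair on attribution, and 12.1 requires sign-off by the Protocol Principal Investigator and at least monthly calls with CTEP. This makes divergent decisions by site less likely, but the reviewers still have no single rule to apply.

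**The size may be small.** Checkpoint therapy starts on day 11 of a 42-day window. The nivolumab list puts diabetes with ketoacidosis below 3%; adding 3 points to a 20% base gives 0.20842 + 0.37354 = 0.582. That is a fair lower illustration for one event. The lists give broad frequency bands, not cycle 1 DLT rates.

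**Appendix D cannot be checked.** Its endocrine algorithm is a figure not reproduced in the text reviewed, so whether it settles any of this is unknown.

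**Conclusion.** The point holds for two groups: diabetes or insulin-managed hyperglycemia, and grade 3 hypopituitarism (with any pituitary-related adrenal deficiency) on stable replacement. For these, the stopping rules that feed the DLT definition conflict or leave the classification open. It should be corrected.

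A reader might infer that grade 3-4 endocrine events in general both are and are not DLTs. The documents do not support that. Thyroiditis and isolated thyroid or testosterone deficiency are treated consistently, symptomatic hypophysitis is grade 3 in both places, and 6.3.2 gives no explicit grade 4 permission. Exception A and the NOTE also reach only laboratory and electrolyte abnormalities.

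A reader might also infer that A1 was wrongly declared the MTD. Section 5.2.1 reports 1 DLT in 6, and one more would have made 2 in 6 and failed the rule. But nothing shows that a disputed event occurred there. The fall from 0.655 to 0.534 or 0.420 is a sensitivity range resting on an assumed 20% base and an assumed 5 or 10 added points.

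**What to change.** Reconcile exception A of 5.4, the restart wording of 6.3.2, the pancreatitis and endocrine tables of 6.3.3 with their footnotes, and the NOTE in 6.3.4. Each of these should end with one discontinuation status by grade and one DLT status stated in 5.4:
- DM and insulin-managed hyperglycemia, with the line between them defined.
- Hypopituitarism and adrenal insufficiency on replacement.

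Section 5.4 should also say whether exception A covers a clinical diagnosis or only a laboratory value. Which clinical rule to adopt is for the sponsor and investigators; this review takes no view.

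Then check whether any cycle 1 event already scored falls in either group and, if so, re-adjudicate it under the reconciled text. The cost is wording in four sections and a short check of existing records, with no additional patients.

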6.3.3 Dose Modifications for Nivolumab-/Ipilimumab-Related Toxicity

NOTE: No dose reductions apply to nivolumab or ipilimumab, only dose delays. The above dose delay criteria/time frames apply for nivolumab-/ipilimumab-related toxicity.

For information on specific toxicity and management plans for nivolumab or nivolumab/ipilimumab combination treatment, see below and reference management guidelines/algorithms in Appendix D, as noted.

Skin Rash and Oral Lesions	Management/Next Dose for Nivolumab and Nivo/Ipi Combination
≤ Grade 1	No change in dose *
Grade 2	No change in dose *
Grade 3	Hold* until ≤ Grade 1. Resume at same level at investigator discretion
Grade 4	Off protocol therapy
*Patients with purpuric or bullous lesions must be evaluated for vasculitis, Steven-Johnson syndrome, TEN, and autoimmune bullous disease including oral lesions of bullous pemphigus/pemphigoid. Pruritus may occur with or without skin rash and should be treated symptomatically if there is no associated liver or GI toxicity. Note skin rash typically occurs early and may be followed by additional events particularly during steroids tapering.	
Recommended management: AE management guidelines	

Liver Function AST, ALT, Bilirubin	Management/Next Dose for Nivolumab and Nivo/Ipi Combination
≤ Grade 1	No change in dose.
Grade 2	Hold until UNL or baseline. Resume at same dose level.
Grade 3	Off protocol therapy
Grade 4	Off protocol therapy
Continued treatment of active immune mediated hepatitis may exacerbate ongoing inflammation. Holding drug to evaluate LFT changes and early treatment are recommended. LFT changes may occur during steroid tapers from other events and may occur together with other GI events including cholecystitis/pancreatitis.	
Recommended management: see Hepatic AE management algorithm	

Diarrhea/ Colitis	Management/Next Dose for Nivolumab and Nivo/Ipi Combination
≤ Grade 1	No change in dose
Grade 2	Hold until baseline. No change in dose
Grade 3	Off protocol therapy.
Grade 4	Off protocol therapy

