
Distinguishing inflammatory pneumonitis is often a diagnosis of exclusion for patients who do not respond to antibiotics and have no causal organism identified including influenza. Most patients with respiratory failure or hypoxia will be treated with steroids. Bronchoscopy may be required and analysis of lavage fluid for lymphocytic predominance may be helpful. Patients with new lung nodules should be evaluated for sarcoid like granuloma. Please consider recommending seasonal influenza killed vaccine for all patients.
	

Recommended management: See Pulmonary Adverse Event Management Algorithm
	

Other GI N-V	Management/Next Dose for Nivolumab
≤ Grade 1	No change in dose.
Grade 2	Hold pending evaluation for gastritis duodenitis and other immune adverse events or other causes. Resume at same dose level after resolution to ≤ Grade 1.
Grade 3	Hold pending evaluation until ≤ Grade 1. Resume at same dose level. If symptoms do not resolve within 7 days with symptomatic treatment patients should go off protocol therapy
Grade 4	Off protocol therapy
Patients with grade 2 or 3 N-V should be evaluated for upper GI inflammation and other immune related events.	

Cardiac Toxicities*	Management/Next Dose for Nivolumab and Nivo/Ipi Combination
≤ Grade 1	Hold dose pending evaluation and observation.** Evaluate for signs and symptoms of CHF, ischemia, arrhythmia or myositis. Obtain history EKG, CK (for concomitant myositis), CK-MB. Repeat troponin, CK and EKG 2-3 days. If troponin and labs normalize may resume therapy. If labs worsen or symptoms develop then treat as below. Hold pending evaluation.
Grade >2 with suspected myocarditis	Hold dose.** Admit to hospital. Cardiology consult. Rule out MI and other causes of cardiac disease. Cardiac Monitoring. Cardiac Echo. Consider cardiac MRI and cardiac biopsy. Initiate high dose methylprednisolone. If no improvement within 24 hours, add either infliximab, ATG or tacrolimus. Consult algorithm for more details. Resume therapy if there is a return to baseline and myocarditis is excluded or considered unlikely.
Grade >2 with confirmed myocarditis	Off protocol therapy. Admit to CCU (consider transfer to nearest Cardiac Transplant Unit). Treat as above. Consider high dose methylprednisolone Add ATG or tacrolimus if no improvement. Off treatment.

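### The suspected-myocarditis row in 6.3.3 adds a non-steroid immunosuppressant and then lets nivolumab/ipilimumab resume, without repeating the 6.3.2 and 6.3.4 rule that stops such patients

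*Combined protocol and SAP*

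**What the plan says.** The cardiac table in 6.3.3 has a row for grade >2 toxicity with suspected myocarditis. Dosing is held and high-dose methylprednisolone is started. Then: "If no improvement within 24 hours, add either infliximab, ATG or tacrolimus". The row ends: "Resume therapy if there is a return to baseline and myocarditis is excluded or considered unlikely". The next row, for confirmed myocarditis, also names ATG or tacrolimus, but takes the patient off treatment.

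Two general rules cover the same step. Section 6.3.2 says "Any patients who require additional immune suppressive treatment beyond steroids should go off study treatment". Section 6.3.4 opens with "Nivolumab and ipilimumab treatment should be discontinued if any of the following criteria are met", and its list includes "Any subjects who require additional immune suppressive treatment beyond steroids should go off study treatment".

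Section 6.3.2 also has two steroid rules. The first is "Patients requiring high dose steroid treatment for autoimmune or inflammatory events should go off study treatment except for a short course of tapering steroids", with the exception limited to infusion reaction, skin rash or endocrine events. The second is a way back for a patient started on corticosteroids who "is determined to not require steroid treatment for an autoimmune adverse event may resume therapy after a 2-week observation period without further symptoms". The note at the head of 6.3.3 adds: "The above dose delay criteria/time frames apply for nivolumab-/ipilimumab-related toxicity".

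Section 6.3.1, in its paragraph on continuing nivolumab alone after a grade 2 or 3 event on the combination, removes patients with renal, CNS, cardiac or pulmonary toxicity from study. The parallel sentence in 5.9 omits cardiac.

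**The concern.** The row prescribes a second immunosuppressant and then gives a resume instruction that does not separate patients who needed that agent from those who did not. Staff managing an acute cardiac event will work from the row. It neither states nor cites the limit in 6.3.2 and 6.3.4. It refers to an algorithm for detail, but the title of Appendix D lists no cardiac algorithm.

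The main stake is safety: re-dosing a patient whom 6.3.4 stops, after a suspected toxicity that the table's own footnote links to deaths.

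The second stake is the DLT count. Section 5.4 defines a non-hematologic DLT through permanent discontinuation under 6.2.2 and 6.3.4. An event that a site handles as hold-and-resume may not be recognised as one that 6.3.4 says should have ended treatment.

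**Working it through.** **1. The rules side by side.**

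| Place | Situation | Instruction |
|---|---|---|
| 6.3.3, suspected myocarditis | Steroids, then infliximab, ATG or tacrolimus | Resume at baseline if myocarditis excluded or thought unlikely |
| 6.3.3, confirmed myocarditis | Steroids, then ATG or tacrolimus | Off treatment |
| 6.3.2 | Immune suppression beyond steroids required | Off study treatment |
| 6.3.4 | Same, as one criterion in a list | Discontinue nivolumab/ipilimumab |

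The suspected-myocarditis row is the only resume instruction in 6.3.3 that follows a non-steroid immunosuppressant. Pneumonitis grade 2, endocrine grade 2 and renal grades 2 and 3 also allow resumption, but each prints its two-week steroid condition in the row.

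**2. Which rule controls.** In 6.3.4 any one criterion is enough. Discontinuation under 6.3.3 and immune suppression beyond steroids are separate items, so 6.3.4 adds to the tables. The way back in 6.3.2 is written for corticosteroids only. The better reading is that 6.3.4 overrides the row.

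**3. When the DLT count is touched.** Under 5.4 the event must be treatment-related, grade 3 or higher (the row's grade >2 meets this), after the blinatumomab-only run-in, and no later than day 42. The exposed window, from first checkpoint-inhibitor dose to day 42, is:
- start on day 11: 42 − 11 + 1 = 32 days
- start on day 15: 42 − 15 + 1 = 28 days
- start on day 25: 42 − 25 + 1 = 18 days

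**4. What one uncounted DLT does.** Section 13.4.1 uses a beta(1,2) prior and holds enrollment if Pr(risk > 0.30) is at least 0.70. After x DLTs in n patients the posterior is beta(1+x, 2+n−x).
- 2 of 4: beta(3,4) gives 0.744, and 3 of 6: beta(4,5) gives 0.806. Both match the plan.
- With one uncounted, 1 of 4: beta(2,5) gives 0.420, and 2 of 6: beta(3,6) gives 0.552. Enrollment continues.

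In escalation (5.2.1), 2 of 6 fails the level and 1 of 6 is the MTD. One missed event changes that decision only if exactly one other DLT occurs among the other five patients, with probability 5p(1−p)⁴: 0.328, 0.402 and 0.396 for assumed other-DLT rates p of 0.10, 1/6 and 0.25.

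**5. How often.** The documents give no rate, so the per-patient rate q is an assumption. The chance of at least one event in six is 1 − (1−q)⁶. Acceptance is P(at most 1 DLT in 6), at rate p if every such event is missed and p + q if every one is counted. With p = 1/6:

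| q | At least one in 6 | Accept, missed | Accept, counted | Difference |
|---|---|---|---|---|
| 0.1% | 0.6% | 73.7% | 73.4% | 0.2 points |
| 0.5% | 3.0% | 73.7% | 72.5% | 1.2 points |
| 1% | 5.9% | 73.7% | 71.3% | 2.4 points |

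Differences are taken before rounding. At q = 1% the difference is 2.0 points for p = 0.10 (88.57% to 86.55%) and 2.4 for p = 0.25 (53.39% to 51.04%). These figures treat every event as treatment-related, in the window and missed.

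**The case against.** **The plan already settles the matter.** On this view 6.3.4 stops treatment on any one criterion, 6.3.2 says the same, and the note heading 6.3.3 carries the earlier criteria forward, so only a cross-reference is missing. Most of this stands. A reader might infer that the protocol affirmatively permits re-dosing after a second agent, or that it has no controlling rule. The documents do not support either: the row is silent on that patient and 6.3.4 is not. What remains is that the row prescribes the agent and then tells the site to resume, while the note speaks of delay criteria and time frames without naming the off-treatment rule.

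**Needing an agent is not the same as being given one.** Sections 6.3.2 and 6.3.4 speak of patients who require further suppression, and a patient treated empirically may prove to have an infarction. This stands as a reason to keep the plan's term in the fix. It does not remove the conflict, because 6.3.2 writes an exception for steroids alone. For the same reason, the row's silence on the two steroid rules is an omission, not a contradiction; those rules can be applied alongside it.

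**The DLT effect is buffered.** Section 5.4 requires relatedness, allows toxicity with a clear unrelated cause to be set aside, and asks for Protocol Chair consultation in all cases. Section 12.1 requires PI sign-off on dose decisions and at least monthly calls with CTEP. This stands. However, the row itself requires no consultation before re-dosing.

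**Conclusion.** The conflict is real and sits in the current text, but it is narrow. On the better reading 6.3.4 already stops these patients; the risk is that a site acts on the row alone. The consequence that justifies a change is re-dosing after a potentially fatal toxicity. The DLT consequence needs a related, grade 3 or higher event inside an 18- to 32-day window that also escapes review. At the assumed rates it moves dose-level acceptance by at most 2.4 points.

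Two further inferences are tempting and unsupported. A reader might conclude that the DL A1 result (1 DLT in 6) is in doubt; nothing in the documents shows that such an event occurred there. A reader might also take the <3% category for myocarditis in the nivolumab and ipilimumab risk lists as a ceiling on the event rate. Suspected cases in which myocarditis is later excluded are not a subset of myocarditis, so the lists set no ceiling, and the 0.1% to 1% range is illustrative only.

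Priority lies between worth considering and recommended, on grounds of patient safety and not of any effect on the MTD.

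**What to change.** Replace the last sentence of the row with: 'Resume therapy only if there is a return to baseline, myocarditis is excluded or considered unlikely, and the 6.3.2 steroid conditions (including the 2-week observation period) are met. Patients who required infliximab, ATG, tacrolimus or other immune suppression beyond steroids do not resume nivolumab/ipilimumab (6.3.2, 6.3.4) and are assessed for DLT under 5.4.'

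State how the 6.3.1 sentence removing patients with cardiac toxicity applies to this row, without loosening it, and add cardiac to the parallel sentence in 5.9. Section 5.4 needs no change. Apply the amendment prospectively.

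The cost is a few sentences of text, with no new data, visits or patients. The downside is that a patient who needed a second agent, and in whom myocarditis is later excluded, loses nivolumab/ipilimumab. Section 6.4 lets blinatumomab continue after discussion with the Protocol Chair, subject to the scope given to 6.3.1. The loss of nivolumab/ipilimumab is what 6.3.4 already requires; the amendment only makes it visible where the decision is taken.
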